2.2.3.3 Data and Safety Monitoring Board

An independent DSMB is established and has responsibility for safeguarding the interests of study participants, assessing the safety and efficacy of study procedures, and for monitoring the overall conduct of the study. The DSMB is an independent group advisory to the Sponsor, and is required to provide recommendations about starting, continuing, and stopping the study. In addition, the DSMB is asked to make recommendations, as appropriate, to the Sponsor about:

- Efficacy of the study intervention
- Benefit/risk ratio of procedures and participant burden
- Selection, recruitment, and retention of participants
- Adherence to protocol requirements
- Completeness, quality, and analysis of measurements
- Amendments to the study protocol and consent forms
- Performance of individual centers and core labs
- Participant safety, and
- Notification of and referral for abnormal findings

Details of DSMB operations are defined in the DSMB Charter document.

2.3 Sample Size Justification

The required sample size for the study was estimated using the following assumptions:

- Test basis: Kaplan-Meier estimate of cumulative patency rate at 6 months, with exact binomial estimation for purposes of sample size
- Type I error (alpha): 0.025 (one-sided)
- Statistical power: 80%
- Performance Goal (PG): 75%
- Expected cumulative patency for InterGraft at 6 months: 84.6%.

Based on the above assumptions, a total of 146 evaluable subjects would be required to compare observed cumulative patency to a PG of 75%. With an expected loss-to-follow-up rate of 8% over 6 months, a total of 158 subjects would need to be enrolled in the evaluation phase.

2.4 Study Duration and Termination

Enrollment is expected to occur over a 24-month period. With a minimum of 6-month follow-up and 2-month period of data analysis and regulatory submission preparation, the total duration of the study is expected to be 32 months.

The study may be terminated at any time for reasons of safety, based on a recommendation by the DSMB, an IRB/Ethics Committee, or based on other considerations by the sponsor. Serious, device related or possibly related adverse events that are unexpected in either frequency or type may prompt a review by the principal investigator, Medical Monitor and Sponsor, and may lead to consideration of stopping the study. Such a review and discussion will be documented and included with the study records.

3.0 PROTOCOL

Enrollment in the study is determined at the time of surgery, after the physician has confirmed that inclusion criteria have been met, subjects have no exclusion criteria, and the final inclusion criterion has been met (e.g., target vessels are suitable for connection to a graft using the Venous InterGraft™ Connector and a sutured arterial anastomosis.) Enrolled subjects will be assigned a unique study subject identification number.

3.1 Study Population

The following inclusion and exclusion criteria must be met for enrollment in the study:

Initial Inclusion Criteria (All must be answered YES for study eligibility.)

1. Subject is \geq 18 years of age.
2. Subject requires the creation of a vascular access graft for hemodialysis, secondary to a diagnosis of End Stage Renal Disease.
3. Subject is able to have the vascular access graft placed in an upper extremity.
4. Baseline imaging shows suitable vascular anatomy/ vessel size for the InterGraft™ Venous Connector and an artery at least 3.5 mm in diameter that is suitable for creating the arterial anastomosis.
5. Subject has a reasonable expectation of remaining on hemodialysis for at least 6 months.
6. Subject or his/her legal guardian understands the study and is willing and able to comply with the dialysis schedule and follow-up requirements.
7. Subject or his/her legal guardian provides written informed consent. NOTE: In accordance with the requirements of some Institutional Review Boards (IRB), where applicable, only those subjects with capacity to consent for themselves will be included. Thus, where required by the IRB, adult individuals who lack capacity to consent for themselves will be excluded from the study.

Final Inclusion Criterion to be applied at the time of surgery (Must be answered YES for enrollment into the study.)

Physician's examination at time of surgery shows no significant vessel lesions, calcification(s), anatomic structures or abnormalities that may limit ability to safely deploy the InterGraft™ Venous Connector or create a sutured arterial anastomosis.

Exclusion Criteria (All must be answered NO for study eligibility.)

1. Subject has a documented and unsuccessfully treated ipsilateral central venous stenosis as determined by imaging.
2. Subject currently has a known or suspected bacterial, fungal, or HIV infection. NOTE: Subjects with hepatitis B or C may be included in the study. .
3. Subject has a known hypercoagulable or bleeding disorder or requires treatment with warfarin or heparin

4. Subject has had a previous instance of Heparin Induced Thrombocytopenia type 2 (HIT-2) or has known sensitivity to heparin.
5. Subject has co-morbid conditions that may limit their ability to comply with study and follow-up requirements.
6. The patient has had >2 previous arteriovenous accesses in treatment arm.
7. Subject is currently taking Aggrenox®.
8. Subject is in need of, or is scheduled for any major surgery within 30 days of the study procedure.
9. Subject is currently taking maintenance immunosuppressant medication such as rapamycin, mycophenolate or mycophenolic acid, prednisone (>10 mg), cyclosporine, tacrolimus or cyclophosphamide.
10. Life expectancy is less than 12 months.
11. Subject is pregnant.
12. Subject is a poor compliance risk (i.e. history of IV or oral drug abuse).
13. The subject is enrolled in another dialysis or vascular investigational study.

3.2 Study Procedures

The study procedure will be performed in accordance with the Instructions for Use (IFU) provided with the study device. A commercially available 6mm diameter synthetic graft will be used. Such grafts may include conventional ePTFE grafts or grafts designed for early cannulation (within 24-48 hours). The study procedure will be performed in an operating room that has fluoroscopic imaging capability for guiding placement of the VIG. The anesthesia regimen will be determined at the physician's discretion; there are no study-specific anesthesia requirements. A regional nerve block is typically performed for placement of an AVG. Standard, routine hemodynamic monitoring will be performed to assess cardiovascular status throughout the procedure. Heparin anticoagulation may be provided at the physician's discretion.

Subjects will be followed at 2 weeks and monthly thereafter through 6 months to assess graft patency and complications. Measurement of access flow rate is part of standard care. Data from routine AV access flow monitoring performed as part of usual care will also be collected. The required schedule for subject treatment and evaluation is shown in **Table 1**.

Table 1: Schedule of Subject Treatment and Evaluation

Timeframe (window)	Test/Procedure
Pre-procedure (within 30 days)	Baseline imaging of target AVG site (performed as part of standard care) Baseline labs: Hgb, Hct, WBC, platelets
Pre-procedure (within 24 hours)	Urine pregnancy test for female subjects with reproductive potential
Immediately following end of AVG implant procedure (before leaving surgery suite)	Confirmation of AVG flow (palpable thrill, audible bruit; In addition, angiogram may be performed at physician's discretion, if warranted.)
Post- procedure (within 48 hours)	Post procedure labs: Hgb, Hct
At discharge	Confirmation of AVG flow (palpable thrill, audible bruit)
2 weeks following the procedure (14 +4/-7 days)	Clinical follow- up with AVG evaluation (includes collection of information regarding subsequent hospitalization and AEs)
30, 60, 90, 120, 150,180 days following the procedure (± 14 days)	Clinical follow- up with AVG evaluation (includes collection of information regarding subsequent hospitalization, AEs, and AVG interventions) AVG flow rate evaluation (ultrasound or similar) is performed at the 90-day and 180-day follow-up visits

The following final events will justify cessation of study follow-up: death, AVG abandonment, lost to follow up (at least 3 attempts to contact the subject should be made and documented), or completion of study follow-up.

3.3 Patient Withdrawal

Patients may withdraw consent from the study at any time. Study data collected prior to withdrawal will be analyzed and included with the final study results. The investigator may withdraw the patient from the study at any time if assessed to be in the best interest of the patient.

3.4 Protocol Violations

A protocol violation is defined as any change, deviation, or departure from the study design or procedures of the research project that is not approved by the IRB and study sponsor prior to its initiation or implementation, OR deviation from standard operating procedures, Good Clinical Practices (GCPs), national or local regulations. Protocol violations may or may not be under the control of the research team or hospital staff.

Major Protocol Violations

All major protocol violations must be reported to the IRB, as applicable and in accordance with local IRB policy, AND to the study sponsor, immediately upon discovering them, and no later than seven (7) calendar days from the time the study team receives knowledge of the event.

A major violation is a protocol violation that meets the following criteria:

- Represent a serious or continuing failure on the part of the study team to comply with the protocol, standard operating procedures, GCPs, federal, state or local regulations;
- Impacts patient safety or substantially alter risks to patients. May or may not result in actual harm (clinical, emotional, social, financial, etc.);
- Significantly damages the completeness, accuracy and reliability of the data collected for the study;
- Is under control of the investigator/research team/hospital staff

4.0 DATA ANALYSIS

The following sections describe statistical analysis procedures and considerations.

4.1 General Statistical Considerations

- a. Descriptive statistics will be used to summarize subject baseline and outcome data collected during the study. Continuous variables will be summarized using means, standard deviations, medians, interquartile ranges, minimums and maximums. Categorical variables will be summarized in frequency distributions.
- b. Statistical analyses will be performed by validated software (e.g., SAS, SPSS, or Cytel Software)
- c. Copies of databases used to prepare clinical report summaries will be archived to enable any statistical analyses performed to be replicated.
- d. A full data listing will be prepared, including an electronic version in a standard computer-accessible format (e.g., SAS) at the completion of the study. Listings of data represented on the case report form (CRF) will be provided for all key baseline, demographic and outcome variables to facilitate further investigation of tabulated values and to allow for clinical review of safety variables.

A one-sided p-value of 0.025 will be considered evidence of statistical significance for the primary study endpoint.

4.2 Analysis Populations

All subjects who meet the enrollment criteria and in whom the VIG InterGraft™ Connector is attempted will be included in the ITT primary analysis population. Roll-in cases will not be included in the main study analyses.

4.3 Primary Endpoint

Cumulative patency at 6 months will be evaluated using the estimated patency from a Kaplan Meier survival analysis. The test statistic will take the following form:

$$\text{Z-test statistic} = (P - 0.75) / \text{SE}(P)$$

Where, (P) represents the Kaplan Meier estimate of cumulative patency at 6 months, and the standard error SE (P) is estimated using the method of Peto *et al* (1977).

Subjects who withdrawn for reasons other than loss of cumulative patency will be included in the analysis up until the time of withdrawal, and be considered censored in the analysis, according to usual convention, after withdrawal.

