If a study subject misses or is unavailable/unwilling to return for the final 6 month follow-up visit, telephone follow-up with the subject or their dialysis center should be attempted to determine the patency status of the AVG at 6 months (the primary study endpoint), and to gather as much additional information as possible in order to complete the 6 month follow up and study completion eCRFs. Telephone follow-up with subjects should be done only if the subject is unwilling or unable to come in. If the subject cannot be reached, then the dialysis center should be contacted (if allowed) in order to determine AVG patency at 6 months. If it is not possible to reach the subject by phone or to contact the dialysis center, then the subject will be considered as lost-to-follow up.

Post-procedure Graft Interventions

As per standard care following the AVG implant procedure, AVG interventions should be avoided within the first 7 days following the index AVG implant procedure. As warranted and determined by the physician, standard balloon angioplasty and thrombectomy procedures may be performed within the AVG, VIG, and adjacent native artery and vein. Mechanical thrombectomy devices that use spinning, rotating or other movable parts should NOT be used in the study, as this may result in entanglement or other damage to the VIG. The balloon diameter used should be equal to that of the VIG diameter and should be no larger than 6mm when used to treat the VIG segment that is within the AVG.

Summary of Tests and Procedures

The required schedule for subject treatment and follow-up evaluation is shown in **Table 1**.

Table 1: Schedule of Subject Treatment and Evaluation

Timeframe (window)	Test/Procedure
Pre-procedure (within 30 days)	Baseline imaging of target AVG site (performed as part of standard care) Baseline labs: Hgb, Hct, WBC, platelets
Pre-procedure (within 24 hours)	Urine pregnancy test for female subjects with reproductive potential
Immediately following end of AVG implant procedure (before leaving surgery suite)	Confirmation of AVG flow (e.g., palpable thrill, audible bruit). At the physician's discretion and if warranted, an angiogram may also be performed to confirm patency.
Post- procedure (within 48 hours)	Post procedure labs: Hgb, Hct
At discharge	Confirmation of AVG flow (palpable thrill, audible bruit)

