2.2.1.1 Choice of Performance Goal

Based on a review of the literature and prior studies of similar AVGs cleared for commercial distribution, the observed cumulative patency rate at 6 months for standard AV graft implants ranged from 65% to 98%. Based on the proposed sample size for the current study (see below) and an expected cumulative patency rate of 84.6% seen for AVGs placed using the VIG in the initial phase, the exact, lower two-sided 95% confidence bound for cumulative patency is estimated to be 79.9%. A comparison to a target Performance Goal (PG) of 75% has been chosen for the evaluation.

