4.9 Sensitivity Analyses

The primary endpoint is cumulative patency at 6 months, defined as the percentage of subjects free from loss of access of the study graft for hemodialysis, assessed at 6 months. Loss of access, including graft abandonment, and the associated time of occurrence will be considered events for purposes of the primary endpoint analysis.

Subjects who have died for reasons unrelated to the study device will be considered as censored with regard to the primary endpoint analysis at the time of death, and their last known status will be used.

Subjects who have become lost to follow-up or who have withdrawn consent for participation in the study prior to 6 months will be considered to have missing primary endpoint outcomes. In the primary analysis, these subjects will be considered to have been censored at the last documented determination of their status prior to study exit. Sensitivity analyses will also be performed to determine the potential impact of these missing data on the primary analysis results, including a tipping point analysis where their status at the time of study exit is assumed to be loss of patency.

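### With day-180 status known, the primary Wald Z-test does not hold its stated one-sided 0.025: type I error is about 0.032 to 0.035 at 158 enrolled with 8% loss

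*SAP*

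**What the plan says.** The only hypothesis test is in SAP 4.3, repeated in protocol 18.0: Z = (P - 0.75)/SE(P), defined thus: "P) represents the Kaplan Meier estimate of cumulative patency at 6 months, and the standard error SE (P) is estimated using the method of Peto". SAP 4.1 sets the criterion: "A one-sided p-value of 0.025 will be considered evidence of statistical significance for the primary study endpoint".

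The study was sized in SAP 2.3 on this footing: "Test basis: Kaplan-Meier estimate of cumulative patency rate at 6 months, with exact binomial estimation for purposes of sample size". The inputs are a 75% goal, 84.6% expected patency and 80% power, which give 146 evaluable subjects and 158 enrolled with 8% loss. SAP 2.2.1.1 illustrates the choice of goal with "the exact, lower two-sided 95% confidence bound for cumulative patency".

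Follow-up visits fall at "30, 60, 90, 120, 150,180 days following the procedure (± 14 days", so a final visit may lawfully take place on days 166 to 179. For subjects who are lost or withdraw, SAP 4.9 says that "these subjects will be considered to have been censored at the last documented determination of their status prior to study exit". For a missed final visit, protocol 11.0 asks for telephone contact "to determine the patency status of the AVG at 6 months (the primary study endpoint". Neither document says how to treat a patent graft whose final visit took place inside the window but before day 180.

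**The concern.** A Wald statistic uses the standard error at the observed rate. For a proportion above one half, that standard error shrinks as the rate rises. A result good enough to pass therefore carries a smaller standard error than the null rate would give, and the test passes too easily. Neither document specifies a null-variance standard error, a transformation or an exact test, and neither checks the actual type I error. The sensitivity analyses in SAP 4.9 concern missing outcomes only.

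This is the sole confirmatory test in a single-arm study intended to support a 510(k) clearance. If it runs above 0.025, a device whose true patency merely equals the goal is declared successful more often than the plan states.

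**Working it through.** **Inputs from the documents.** Goal 0.75, expected rate 0.846, one-sided 0.025, power 80%, 146 evaluable, 158 enrolled, 8% loss (SAP 2.3); the Z statistic (SAP 4.3); censoring (SAP 4.9); visit window (SAP 3.2).

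**Assumptions.** The Peto formula is not printed. It is taken as SE = P × sqrt((1 - P)/r), with r the number at risk. The timing of events and losses is not given and was varied.

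**1. The plan's own sample size.** In the exact binomial at n = 146, the smallest c with P(X ≥ c | 0.75) ≤ 0.025 is c = 120, with tail 0.0249. Power is P(X ≥ 120 | 0.846) = 0.823. The 146 is reproduced. For enrolment, 146 + 12 = 158.

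**2. The written test with complete status.** Without censoring r = nP, so the assumed Peto SE becomes P × sqrt((1 - P)/(nP)) = sqrt(P(1 - P)/n), the binomial SE. At 119/146:

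- P = 0.8151 and SE(P) = sqrt(0.8151 × 0.1849/146) = 0.0321
- SE under the null = sqrt(0.75 × 0.25/146) = 0.0358
- Z = 0.0651/0.0321 = 2.03, above 1.96, so the test passes
- Wald lower limit 75.2%; exact two-sided 95% lower bound 74.2%
- type I error P(X ≥ 119 | 0.75) = 0.0395; power 0.874

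**3. Other sizes, complete status.** The same enumeration at all 44 sizes from 130 to 173 gives 0.028 to 0.045, above 0.025 every time. It is 0.0358 at 147 and 0.0301 at 158 (cut-off 129).

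**4. The planned case, day-180 status known.** Kaplan-Meier simulation with 158 enrolled, 8% loss and true 180-day patency 0.75 (40,000 to 60,000 runs, Monte Carlo SE 0.0007 to 0.0009). Nine patterns were used: constant, early or late events, crossed with exponential, uniform or late loss.

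- Written test: type I error 0.032 to 0.035, whichever way r is counted; power at 0.846 is 0.864 to 0.870
- Same test with the Greenwood SE: 0.034 to 0.038
- Logit-scale limit with the Greenwood SE: 0.021 to 0.024; power 0.812 to 0.825

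A separate set of runs that included early loss gave 0.032 to 0.037 for the written test. With a further 5 to 10% censored by unrelated death (assumed), the written test gives 0.031 to 0.033.

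**5. If patent grafts last seen on days 166 to 179 are censored at that visit.** Constant hazard, 158 enrolled, 8% loss; cells show type I error / power.

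| Final visits | Written test, r at day 180 | Written test, r just after last event | Logit with Greenwood |
|---|---|---|---|
| 25% early | 0.018 / 0.80 | 0.027 / 0.83 | 0.021–0.022 / 0.80–0.82 |
| Spread evenly over window | about 0.007 / 0.64–0.65 | about 0.026 / 0.79 | about 0.022 / 0.80 |

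With an even spread and r counted at day 180, about 16% of simulated trials at 84.6% patency change from fail to pass under the logit rule, and none the other way.

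**The case against.** **The inflation depends on a reading.** It is shown only when day-180 status is known. Under early-visit censoring the written test can be conservative, as step 5 shows. This stands, and the point is limited accordingly. The known-status reading is the natural one, since the endpoint is assessed at 6 months and protocol 11.0 goes to some length to establish status then. It is not written down, however, so a reader should not infer that the test is liberal in every case.

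**The documents do not contradict themselves.** A reader might set the exact sizing and the exact bound against the Wald test and call it a conflict. The text does not support that. SAP 2.3 confines the exact binomial to sample size, SAP 2.2.1.1 uses the exact bound as an illustration at the expected rate, and both documents name the same Z-test. Sizing by one method and testing by another is an approximation. What fails is the stated error rate.

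**0.0395 is not the planned analysis.** It belongs to 146 complete cases and lies toward the upper end of a sawtooth. The plan enrols 158 and keeps lost subjects in as censored.

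**The Peto formula is assumed.** This also stands. The planned-case figure rests on it, and the enumeration needs it to reduce to the binomial SE without censoring, as the assumed form does.

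**Conclusion.** The point holds for day-180 status known. Under planned enrolment and loss, type I error is about 0.032 to 0.035 against a stated 0.025. At 0.033 the excess is 0.8 percentage points, or 0.008/0.025, roughly 30% in relative terms. With complete data the excess appears at every size from 130 to 173. At 146 it amounts to one subject: 119 passes, although the exact bound does not clear the goal.

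The size is modest, but this is the only confirmatory test, so it should be fixed. The planned-case figure rests on the assumed Peto formula and on assumed event and loss timing, which moves it little. No direction is claimed if early in-window visits are censored. There the result turns on two things the documents leave open: the status rule, and the time at which the number at risk is counted.

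**What to change.** Make one dated amendment before the primary data are analysed.

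1. **Protocol 18.0 and SAP 4.3.** Use a test that holds about 0.025. One option is to declare success if the lower limit of the two-sided 95% logit-scale Kaplan-Meier interval, with the Greenwood SE, exceeds 75%. With complete data at 146 the limit is 74.4% at 119 and 75.1% at 120, so the cut-off is 120, the same as in the exact sizing (type I error 0.0249, power 0.823). It keeps the Kaplan-Meier estimate and does not need the unprinted Peto formula. A null-variance test also gives 120/146. Changing only the SE to Greenwood is not enough.
2. **SAP 4.9.** State whether a patent graft last seen on days 166 to 179 is carried to day 180 or censored at that visit. This must go in the same amendment. If such visits are censored and the number at risk is counted at day 180, the logit rule makes success easier than the written test (evenly spread visits: type I error about 0.007 to 0.022, power about 0.64 to 0.80). With 30 primary-population subjects already enrolled (protocol Table 3), that choice should not be left until results are seen.
3. **SAP 1.0.** Update the statement that the analyses otherwise match Versions 1 and 2.

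**Cost.** No extra subjects are needed to keep 80% power when status is known. Power falls from 0.874 to 0.823 at 146, and from about 0.865 to about 0.82 at 158 with 8% loss. It would be about 0.79, just under target, if a further 10% were censored by unrelated death (assumed). The logit limit is itself approximate. With complete data it exceeds 0.025 at 7 of the 44 sizes (maximum 0.0267), against 10 of 44 for the null-variance test (maximum 0.0277) and 44 of 44 for the written test.
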